7.6.3. Treatment Accountability

All drug accountability records must be kept current.

The investigator must be able to account for all opened and unopened study drug. These records should contain the dates, quantity, and study drug:

- dispensed to each patient,
- returned from each patient (if applicable), and
- disposed of at the site or returned to the sponsor or designee.

All accountability records must be made available for inspection by the sponsor and regulatory agency inspectors; photocopies must be provided to the sponsor at the conclusion of the study.

7.6.4. Treatment Compliance

Patients will be dosed under the supervision of appropriate study personnel. All study drug compliance records must be kept current and made available for inspection by the sponsor and regulatory agency inspectors.

7.7. Concomitant Medications and Procedures

Any treatment administered from the time of informed consent to the final study visit will be considered concomitant medication. This includes medications that were started before the study and are ongoing during the study.

Information on concomitant medication for each patient will be recorded at each study visit from screening through the end of study.

7.7.1. Prohibited Medications and Procedures

Treatment with the following concomitant medications is prohibited during the study. Study drug will be immediately discontinued if any of the following are used during the study (see Section 7.4.2.1):

- Treatment with a live (attenuated) vaccine (a list of examples of such vaccines is below):
 - Chickenpox (Varicella)
 - FluMist-Influenza
 - Intranasal influenza
 - Measles (Rubeola)

- Measles-mumps-rubella combination
- Measles-mumps-rubella-varicella combination
- Mumps
- Oral polio (Sabin)
- Oral typhoid
- Rubella
- Smallpox (Vaccinia)
- Yellow fever
- Bacillus Calmette-Guerin
- Rotavirus
- Varicella Zoster (shingles; ie, Zostavax)
- Treatment with an investigational drug (other than REGN3500)
- Treatment with immunomodulating biologics
- Treatment with systemic non-steroidal immunosuppressant (may be used as rescue, see Section 7.3 for details)
- Treatment with systemic corticosteroids (may be used as rescue, see Section 7.3 for details)
- Treatment with TCS or TCI (may be used as rescue in which study drug will not be discontinued, see Section 7.3 for details)
- Treatment with topical crisaborole (may be used as rescue in which study drug will not be discontinued, see Section 7.3 for details)
- Initiation of treatment of AD with prescription moisturizers

The following concomitant procedures are prohibited during study participation:

- Major elective surgical procedures
- Phototherapy (ultraviolet A [UVA], ultraviolet B [UVB], narrowband UVB [nbUVB], high dose UVA, and psoralen and UVA [PUVA])
- Tanning in bed/booth

7.7.2. Permitted Medications and Procedures

Other than the prohibited medications listed in Section 7.7.1, treatment with concomitant medications are permitted during the study. This includes basic skin care (cleansing and bathing, including bleach baths), bland emollients (required as background treatment; however, bland emollients should not be applied on any area(s) of lesional or non-lesional skin designated for assessment for at least 8 hours before each clinic visit), topical anesthetics, and antihistamines for any duration, and oral antibiotics for up to 14 days. Medications used to treat chronic disease such as diabetes, hypertension, and asthma are also permitted; if there is any question regarding whether

a concomitant medication may be used during the study, the study site should contact the medical monitor.

7.7.2.1. Prohibited Concomitant Medications or Procedures as Rescue Treatment

If medically necessary (ie, to control intolerable AD symptoms), study patients may receive rescue treatment for AD at the discretion of the investigator (see Section 7.3). If a patient receives rescue treatment with systemic corticosteroids or non-steroidal systemic immunosuppressive drugs, study treatment will be permanently discontinued immediately. If rescue treatment consists of topical medications, the patient can continue study treatment.

Blinded adjudication of concomitant medications may be performed to identify concomitant medications that confound study endpoints.

8. STUDY SCHEDULE OF EVENTS AND PROCEDURES

8.1. Schedule of Events

Study assessments and procedures are presented by study period and visit in [Table 2](#).

Table 2: Schedule of Events

	Screening Period ^{13, 14}	Double-Blind Treatment Period									Follow-Up Period					Un-sch ¹⁶	ET ¹⁹
In-clinic Visit (V) Study Procedure ¹	V1	Baseline V2	V3	V4	V5	V6	V7	V8	V9	EOT V10	V11	V12	V13	V14	EOS V15		
Week (W)	-	-	W2	W4	W6	W8	W10	W12	W14	W16	W20	W24	W28	W32	W36	-	-
Day (D)	D-35 to D-1	D1	D15	D29	D43	D57	D71	D85	D99	D113	D141	D169	D197	D225	D253	-	-
Visit Window in Days	-	-	±3	±3	±3	±3	±3	±3	±3	±3	±3	±3	±3	±3	±3	-	-
Screening/Baseline:¹																	
Inclusion/Exclusion	X	X															
Informed Consent	X																
Medical History/ Demographics	X																
Ocular History ⁸	X																
Patient e-diary Training (Pruritus, Pain, and Sleep Quality NRS Assessments and Emollient Use) ²	X																
Randomization		X															
Treatment:¹																	
Review patient e-diary data		X ¹⁵	X	X	X	X	X	X	X	X	X	X	X	X	X	X	X
Study Drug Administration/ Dispensing/ Accountability ³		X	X	X	X	X	X	X	X								
Concomitant Meds/ Procedures	X ¹⁴	X	X	X	X	X	X	X	X	X	X	X	X	X	X	X	X
Efficacy:¹																	
Pruritus, Pain, and Sleep Quality NRS (daily) ⁴	X	X	X	X	X	X	X	X	X	X	X	X	X	X	X	X	X
Patient-reported HADS, DLQI, POEM ^{5,6}	X	X	X	X		X		X		X		X		X	X	X	X
EASI, IGA, GISS, SCORAD, BSA ⁵	X	X	X	X	X	X	X	X	X	X	X	X	X	X	X	X	X

	Screening Period ^{13, 14}	Double-Blind Treatment Period									Follow-Up Period						
In-clinic Visit (V) Study Procedure ¹	V1	Baseline V2	V3	V4	V5	V6	V7	V8	V9	EOT V10	V11	V12	V13	V14	EOS V15	Un-sch ¹⁶	ET ¹⁹
Week (W)	-	-	W2	W4	W6	W8	W10	W12	W14	W16	W20	W24	W28	W32	W36	-	-
Day (D)	D-35 to D-1	D1	D15	D29	D43	D57	D71	D85	D99	D113	D141	D169	D197	D225	D253	-	-
Visit Window in Days	-	-	±3	±3	±3	±3	±3	±3	±3	±3	±3	±3	±3	±3	±3	-	-
Safety:¹																	
Vital Signs ⁷	X	X	X	X	X	X	X	X	X	X	X	X	X	X	X	X	X
Physical Exam	X									X					X	X	X
ECG	X									X					X	X	X
Weight	X	X								X					X	X	X
Height	X																
Ophthalmological Exam ⁸	X															X ¹⁷	
Adverse Events	X	X	X	X	X	X	X	X	X	X	X	X	X	X	X	X ¹⁸	X
Laboratory Testing:^{1,11}																	
Hematology, Chemistry	X	X		X		X		X		X	X	X	X	X	X	X	X
Serologies (HIV Ab, HBsAg, HBcAb, HCV Ab)	X																
TB QuantiFERON Testing ⁹	X																
Serum FSH (confirm menopausal status)	X																
Pregnancy Test (WOCBP only) ¹⁰	Serum	Urine		Urine		Urine		Urine		Serum	Urine	Urine	Urine	Urine	Serum	Urine	Serum
Urinalysis	X	X		X		X		X		X		X		X	X	X	X
PK and ADA Samples:^{1,11}																	
Serum REGN3500 Concentration (PK)		X	X	X		X		X		X	X	X	X	X	X	X ¹⁸	X
Anti-REGN3500 Antibody (ADA) ²⁰		X								X					X	X ¹⁸	X
Biomarkers:^{1,11}																	
hs-CRP, SAA	X	X		X		X		X		X				X	X	X	X
TARC	X	X		X		X		X		X				X	X	X	X
Total IgE	X	X		X						X					X	X	X
Total IL-33		X	X	X		X		X		X	X	X	X	X	X	X	X
FBR Samples (serum/plasma)	X	X		X		X		X		X				X	X	X	X

	Screening Period ^{13, 14}	Double-Blind Treatment Period									Follow-Up Period						
In-clinic Visit (V) Study Procedure ¹	V1	Baseline V2	V3	V4	V5	V6	V7	V8	V9	EOT V10	V11	V12	V13	V14	EOS V15	Un-sch ¹⁶	ET ¹⁹
Week (W)	-	-	W2	W4	W6	W8	W10	W12	W14	W16	W20	W24	W28	W32	W36	-	-
Day (D)	D-35 to D-1	D1	D15	D29	D43	D57	D71	D85	D99	D113	D141	D169	D197	D225	D253	-	-
Visit Window in Days	-	-	±3	±3	±3	±3	±3	±3	±3	±3	±3	±3	±3	±3	±3	-	-
Genomics Sample: ^{1, 11}																	
Whole Blood DNA ¹²		X															
Whole Blood RNA ¹²		X								X					X		X

ADA: anti-drug antibody; BSA: body surface area; D: day; DLQI: Dermatology Life Quality Index; EASI: Eczema Area and Severity Index; ECG: electrocardiogram; e-diary: electronic patient diary; EOS: end-of-study; EOT: end-of-treatment; ET: early termination; FBR: Future Biomedical Research; FSH: follicle-stimulating hormone; GISS: Global Individual Signs Score; HADS: Hospital Anxiety and Depression Scale; HBcAb: hepatitis B core antibody; HBsAg: hepatitis B surface antigen; HCV Ab: hepatitis C virus antibody; HIV Ab: human immunodeficiency virus antibody; hs-CRP: high-sensitivity C-reactive protein; ICF: informed consent form; IGA: Investigator’s Global Assessment; IgE: immunoglobulin E; IL: interleukin; Meds: medications; NRS: Numerical Rating Scale; PK: pharmacokinetic; POEM: Patient Oriented Eczema Measure; SAA: serum amyloid A; SCORAD: SCORing Atopic Dermatitis; TARC: thymus and activation-regulated chemokine (CCL17); V: visit; Unsch: unscheduled visit; W: week; WOCBP: women of childbearing potential.

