8. Ophthalmological exams at screening are limited to those patients who have a history of certain eye disorders (conjunctivitis, blepharitis or keratitis) within the last 12 months. Exams must be performed by an ophthalmologist (preferably with expertise in Cornea and External Eye Disease [‘front-of-the-eye’] subspecialty expert). Further evaluation will be performed including any additional tests, if applicable, as per the discretion of the ophthalmologist.
9. Tuberculosis QuantiFERON testing at screening will be performed.
10. Not required if postmenopausal status confirmed at screening.

11. Blood samples collected before the administration of study drug. Pharmacokinetic samples will be collected for the determination of REGN3500 concentration and ADA samples for the immunogenicity assessment of REGN3500. In the event of suspected SAEs, such as anaphylaxis or hypersensitivity, additional PK and ADA samples may be collected at or near the event. At the visits where ADA samples are to be taken, the sample should be collected with the PK sample.
12. One whole blood sample to extract DNA for pharmacogenomics analyses should be collected on day 1/baseline (visit 2), but can be collected at any visit. Whole blood samples for RNA extraction should be collected according to time points in [Table 2](#).
13. Patients may be re-screened once if they fail the screening evaluation for reasons related to incidental transitory conditions (eg, medication use, concomitant illness, medical condition), unless the reason for the screen failure is related to failing the disease severity inclusion criteria.
14. During the screening period, treatments for AD will be washed out, as applicable, according to eligibility requirements (see Section 6.2).

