15. Clinical sites will check patient data collected on the e-diary. Baseline peak Pruritus NRS score for maximum itch intensity will be determined based on the average of daily NRS scores for maximum itch intensity during the 7 days immediately preceding randomization. A minimum of 4 daily scores out of the 7 days is required to calculate the baseline average score. For patients who do not have at least 4 daily scores reported during the 7 days immediately preceding the planned randomization date, randomization should be postponed until this requirement is met, but without exceeding the 35-day maximum duration for screening. Patients are also required to have applied a stable dose of topical bland emollient (moisturizer) at least twice daily for at least the 7 consecutive days immediately before randomization (ie, baseline/randomization visit would be the eighth day).
16. Unscheduled visits may be necessary to repeat testing following abnormal laboratory results, for follow-up of AEs, or for any other reason (eg, before a rescue medication/procedure is used), as warranted.
17. Patients who experience adverse events of special interest (AESIs) related to eye disorders (refer to Section 9.4.3) must be referred to an ophthalmologist (preferably with expertise in Cornea and External Eye Disease [‘front-of-the-eye’] subspecialty expert). Further evaluation of these AEs will be performed including any additional tests, if applicable, as per the discretion of the ophthalmologist.
18. If the unscheduled visit was due to an AE, collect samples for PK and ADA analysis.
19. Patients who are withdrawn from the study will be asked to return to the clinic for ET assessments.
20. In the event a patient sample is positive in the REGN3500 ADA assay at week 16 or the first time point analyzed, the week 4 PK sample may be analyzed in the ADA assay.

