1.2.4. Modifications from the Statistical Section in the Final Protocol

The current active protocol for countries other than Japan is the protocol amendment 3 and the one for Japan is the protocol amendment 2. As mentioned on Section 1.1, due to lack of efficacy of REGN3500 in this study, Regeneron Pharmaceuticals, Inc and Sanofi have discontinued the REGN3500 atopic dermatitis program and terminated both ongoing AD studies earlier than planned (R3500-AD-1798 and R3500-AD-1805). Due to the decision, not all planned patients were enrolled in the study. For patients who were already enrolled, investigators were instructed to discontinue the study drugs and transition these patients into post-treatment follow-up period for safety assessments. As a result, a large amount of data remained uncollected as not all enrolled

patients completed all planned study visits and study procedures for the assessments of efficacy, ADA, and biomarker endpoints. Only the abbreviated clinical study report will be reported. Therefore, the following will be removed:

- the analyses using ANCOVA model for both the primary analysis and sensitivity analysis in the primary endpoint (ie, percent change in EASI score), secondary endpoints (ie, absolute change in EASI score, absolute change and percent change in pruritus NRS) and other endpoints (ie, absolute change and percent change in pain NRS and sleep quality NRS)
- the analysis using Cochran-Mantel-Haenszel test for both the primary analysis and sensitivity analysis in the binary secondary endpoints (ie, IGA score of 0 or 1, EASI-50, EASI-75, EASI-90, and improvement in pruritus NRS ≥ 4)
- the multiple imputation and last observation carried forward methods for the missing data imputation in efficacy endpoints
- the imputation of missing data to non-responder except that the data is set to missing due to rescue treatment
- the analyses on association between ADA and efficacy endpoints.
- the analysis on the endpoints of BSA, SCORAD, HADS, DLQI, POEM, and GISS.
- the pharmacodynamic analysis set for biomarker analysis.

One change is that the biomarkers will be analyzed based on the full analysis set.

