2.1. Study Design and Randomization

This is a phase 2b, randomized, double-blind, placebo-controlled, parallel-group, dose-ranging study investigating the efficacy, safety, and PK profiles of REGN3500 administered to adult patients with moderate-to-severe AD. Eligible patients must have a documented history of inadequate response or intolerance to treatment with topical AD medications. This study is intended to provide information regarding 4 different REGN3500 monotherapy dosing regimens. Each REGN3500 dosing regimen will be compared with placebo to enable robust assessment of efficacy and safety.

The study duration is up to 41 weeks, including an up to 5-week (ie, 35 days) screening period, 16-week double-blind treatment period, and 20-week post-treatment follow-up period.

Approximately 300 subjects (60 subjects per treatment group) will be recruited and randomized from approximately 60 sites. Approximately 10% of patients are planned to be enrolled in Japan; and that the Japanese patients will be randomized in 2 cohorts: a sentinel cohort of 15 patients and a second cohort of 15 patients. The randomization scheme and procedure of the Japanese patients will be the same as the rest of the patients. Independent Data Monitoring Committee will review of safety data from the first 15 Japanese patients when the 15th patient completes the Day 15 visit.

Figure 1: Study Flow Diagram

D: day; EASI: Eczema Area and Severity Index; EOS: end-of-study; EOT: end-of-treatment; Q2W: every 2 weeks; Q4W: every 4 weeks; Q8W: every 8 weeks; R: randomization; W: week

On 12 February 2020, the Sponsor decided to stop the study. At that time, 129 subjects had been randomized including 6 Japanese patients. The sponsor instructed the investigators to transition all patients in the treatment phase to the twenty-week safety-follow-up period. These patients will stop the treatment and finish the end of treatment assessments before entering into the follow-up period. All patients who were in the screening period, but had not received study investigational medicinal product (IMP), will be screen failed for the reason of sponsor decision to discontinue study.

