4.8. Immunogenicity Variables

The immunogenicity variables are anti-drug antibody (ADA) status and titer at each time-point/visit. Serum samples for anti-REGN3500 antibody bioanalysis will be collected at time points according to visit schedule (Table 1). In the event a patient sample is positive in the REGN3500 ADA assay at week 16 or the first time point analyzed, the week 4 PK sample may be analyzed in the ADA assay.

Immunogenicity will be characterized by ADA responses and titers observed in patients in the ADA analysis set. ADA responses and titer categories are defined as follows:

- ADA Negative, defined as ADA negative response in the REGN3500 ADA assay at all time points, regardless of any missing samples.
- Pre-existing immunoreactivity, defined as either an ADA positive response in the assay at baseline with all post first dose ADA results negative, OR a positive response at baseline with all post first dose ADA responses less than 9-fold for anti-REGN3500 antibody assay over baseline titer levels
- Treatment-emergent response, defined as a positive response in the ADA assay post first dose when baseline results are negative or missing. The treatment-emergent responses will be further characterized as Persistent, Indeterminate or Transient
 - Persistent Response - Treatment emergent ADA positive response with two or more consecutive ADA positive sampling time points separated by at least 16-week period, for anti-REGN3500 antibody assays, with no ADA negative samples in between
 - Indeterminate Response - as a treatment-emergent response with only the last collected sample positive in the ADA assay
 - Transient Response - a treatment emergent ADA positive assay response that is not considered persistent or indeterminate.
- Treatment-boosted response, defined as a positive response in the ADA assay post first dose that is greater than or equal to 9-fold for anti-REGN3500 antibody assay over baseline titer levels, when baseline results are positive
- Titer categories (Maximum titer values)
 - Low (titer <1,000)
 - Moderate ($1,000 \leq \text{titer} \leq 10,000$)
 - High (titer >10,000)

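### SAP 4.8 can call a patient ADA Negative on one early post-dose sample, so after the stop treatment-emergent ADA incidence can be understated by an amount the documents do not let us size

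*Protocol*

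**What the plan says.** **Sampling.** In protocol Table 2 (repeated as SAP Table 1), the row beginning "Anti-REGN3500 Antibody (ADA" is marked at baseline, EOT/Week 16 (day 113), EOS/Week 36 (day 253), unscheduled visits and ET. The footnotes in protocol 8.1.1 add:

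- for unscheduled visits: "If the unscheduled visit was due to an AE, collect samples for PK and ADA analysis"
- for withdrawals: "Patients who are withdrawn from the study will be asked to return to the clinic for ET assessments"
- for suspected SAEs: "additional PK and ADA samples may be collected at or near the event"
- for the Week 4 PK sample, an ADA assay that is allowed only conditionally: "In the event a patient sample is positive in the REGN3500 ADA assay at week 16 or the first time point analyzed"

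**Classification.** SAP 3.4 requires one non-missing post-dose ADA result for the ADA analysis set (AAS). SAP 4.8 then defines the negative class: "ADA Negative, defined as ADA negative response in the REGN3500 ADA assay at all time points, regardless of any missing samples". SAP 5.10.1 reports the number and percentage of ADA-negative patients, and SAP 5.11.2 uses the same group as a category in the ADA–safety comparison.

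**The stop.** SAP 2.1 records 129 randomized patients when the sponsor stopped the study on 12 February 2020. Of those still on treatment it says: "These patients will stop the treatment and finish the end of treatment assessments before entering into the follow-up period". SAP 1.2.4 states that "a large amount of data remained uncollected as not all enrolled" patients got through every planned visit, and it names ADA among the affected assessments.

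**The concern.** The ADA table is a crude proportion over patients observed for very different lengths of time, and a patient whose observation ends early counts as event-free. One negative sample shortly after the first dose, with nothing later, carries the same weight as negative samples through to EOS.

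The SAP adapted other parts to the stop: the end of the treatment period (3.2), visit mapping (6.4), and a summary of observation time (5.6.2). It also gives treatment-period TEAE rates per 100 patient-years (5.8.1). Nothing comparable was done for ADA. SAP 4.8 does recognise uncertainty about the last sample for positives, through its indeterminate class, but has no counterpart for negatives.

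Immunogenicity remains a secondary objective (SAP 1.2.2). SAP 1.1 says the drug is still being developed for other diseases, so this ADA rate may be read outside the present study.

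**Working it through.** The documents state no ADA incidence, no number of ADA samples and no ADA missing-data rate, so there is no plan figure to reproduce. The check covers timing, then direction, then a range under stated assumptions.

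**1. When samples fall.** Planned EOT to EOS is 253 − 113 = 140 days, or 20 weeks. SAP 2.1 moves stopped patients into a 20-week follow-up, so planned EOS is about 140 days after EOT:

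| Stopped at | EOT sample, about day | EOS sample, about day |
|---|---|---|
| Week 2 | 15 | 15 + 140 = 155 |
| Week 4 | 29 | 29 + 140 = 169 |
| Week 8 | 57 | 57 + 140 = 197 |

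By protocol Table 1, a patient on 30 mg Q8W who is stopped before Week 8 has had one active dose. A late sample is still planned for every stopped patient. The problem arises only if that sample, and any other late one, is missing.

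**2. Can late samples be missing?** SAP 1.2.4 says ADA assessments were not all completed, but not which ones. Counting 140 days from 12 February 2020 (17 + 31 + 30 + 31 + 30 = 139 days to 30 June) gives 1 July 2020. SAP 5.5 provides for COVID-19-related discontinuation in the disposition table. Missed EOS visits are therefore foreseen but not counted.

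**3. Direction.** Under SAP 4.8 any positive post-dose sample, with baseline negative or missing, makes a patient treatment-emergent. A missing late sample can remove a positive but cannot create one. The Week 4 reflex assay follows only a positive result, so it cannot recover a missed positive.

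**4. Size, by assumption.** Let

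- p = incidence if every patient in the AAS also had a late sample
- m = share of the AAS with only an early post-dose sample, taken as unrelated to ADA status
- s = share of eventual positives already positive at that early sample

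Observed incidence = p × [1 − m × (1 − s)], so the relative loss is m × (1 − s), whatever p is. With p = 10% (assumed):

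| m | s = 0 | s = 0.5 | s = 1 |
|---|---|---|---|
| 0 | 10% | 10% | 10% |
| 10% | 9.0% | 9.5% | 10% |
| 25% | 7.5% | 8.75% | 10% |
| 50% | 5.0% | 7.5% | 10% |

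**5. In patients.** 129 / 5 = 25.8 per arm, so one patient is 1 / 25.8 = 3.9 percentage points. The 2.5-point loss at m = 25%, s = 0 is 0.025 × 25.8 = 0.6 of a patient per arm.

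**6. The opposite rule.** SAP 4.8 also counts a positive post-dose result with a missing baseline as treatment-emergent. If 5–10% lack a baseline sample and 2–5% have pre-existing reactivity (both assumed), this adds between 0.05 × 0.02 = 0.1 and 0.10 × 0.05 = 0.5 points.

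**The case against.** The strongest reply is that the plan already provides a late sample. Stopped patients go on to 20 weeks of follow-up ending in an EOS visit with an ADA sample. Those who withdraw are asked back for an ET visit that also carries one, and AE-driven visits add more. Patients with no post-dose result are left out of the AAS, not called negative. This stands. A reader might infer that an early EOT sample by itself biases the rate, or that EOT and EOS are the only post-dose samples; the documents support neither.

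A reader might also infer that some arms will look less immunogenic than others. Nothing shows that. Allocation was blinded and 1:1:1:1:1, there was one stop date, and missingness by arm is not given.

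It can further be said that the consequence is small. SAP 1.1 makes all analyses descriptive, SAP 1.2.4 removes the ADA–efficacy association, and the ADA–safety comparison in SAP 5.11.2 is optional. That limits the importance of the point but does not answer it.

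Finally, SAP 5.5 and 5.6.2 show analysis-set numbers by visit and observation time, and SAP 6.4 relabels the EOT record of stopped patients to their next scheduled visit. These give a partial view. They do not link sampling time to ADA class, and the titer listing in SAP 5.10.1 covers only patients with pre-existing, treatment-emergent or treatment-boosted responses. The last sampling time of negatives is not among the planned ADA displays.

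**Conclusion.** The point holds in a limited form. SAP 3.4 and 4.8 together set no minimum follow-up for a negative classification. Treatment-emergent ADA incidence can therefore be understated, and the ADA-negative group in SAP 5.11.2 can include patients of unconfirmed status. This applies only where the sole post-dose sample is early and there is no EOS, follow-up ET or other late sample.

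It would be tempting to say that incidence is understated. The documents do not support that: they give neither the number of such patients nor how early ADA appears, and the missing-baseline rule pushes the other way. The size is unknown. It is zero if every patient has a late sample or if all eventual positives are already positive at the early one; otherwise the relative loss is m × (1 − s), on assumed values. No hypothesis test is affected. The improvement is cheap and worth making.

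**What to change.** Keep the current all-AAS figure and, around it:

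- In SAP 5.10.1, show on a separate line the patients negative on an early sample only, meaning no EOS, follow-up ET or other sample beyond a time since first dose fixed before database lock. Day 107, where the SAP 6.4 window for Week 16 opens, is one possible cut.
- Report treatment-emergent ADA incidence among late-sampled patients next to the all-AAS figure, with the number late-sampled and the time from first dose to last ADA sample, by arm.
- In SAP 5.11.2, do not pool early-only negatives with confirmed negatives.

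An EOS sample should not be the condition for a negative classification, because that would discard a patient with a negative ET sample late in follow-up.

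The cost is SAP wording plus one extra line and column, using samples already collected. The downside is a smaller denominator for the late-sampled figure, which may also be a selected group and omits early positives without a late sample. That is why both figures should stand side by side.
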